6.5.3. Collection of Information on AEs

The Investigator is required to report all AEs s/he observes directly, as well as all AEs spontaneously reported by the patient, using concise medical terminology. In addition, during the observation period, i.e. from D1 to D18 (or earlier in the event of early discharge) and at each follow-up visit, the patient will be asked a series of questions, and a targeted physical examination will be performed, to investigate any potential AEs.

6.5.4. AE Collection Period

The periods for collection of AEs that occur in the context of the present study are defined as follows:

- For all non-serious adverse events, the observation period extends from the first intake of the study treatment on Day 1 until hospital discharge between D12 and D18;
- For all serious adverse events, the observation period extends from enrolment of the patient in the study, i.e. after signature of the informed consent form, until the end of follow-up (24 months). SAEs will be analysed initially up to 18 months, and then up to 24

months for the additional follow-up period.

All AEs that occur during the AE collection period defined in the protocol must be recorded in the e-CRF, whether or not they are considered to be treatment related. In addition, all AEs that occur after the AE collection period, and that the Investigator considers as possibly related to the study treatment, must also be reported.

6.5.5. Requirements for AE Reporting

Information on AEs must be assessed by a physician. The Investigator must determine whether the AE is considered as serious or not, if necessary with the help of the Coordinating Investigator and the study monitor. This classification will determine the reporting procedure for the event.

All SAEs must be reported immediately, i.e. no later than 24 hours after the Investigator becomes aware of the SAE, to the Swiss TPH clinical study monitor, first by telephone and/or SMS, then by email using the SAE reporting form. This report must include a description of the event, onset date and type, duration, severity, relationship to study treatment (with the help of the Coordinating Investigator as needed), outcome and measures taken, as well as any other relevant clinical or laboratory data. Any additional information must be sent on an SAE follow-up form as it becomes available. Follow-up reports should be submitted as soon as possible, and, if possible, within 5 working days after the new information becomes available. A close-out follow-up report must be sent after the final assessment of the case as "recovered", "recovered with sequelae" [chronicity], "death" etc.

SAEs must also be reported in the AE section of the e-CRF. It should be noted that the reporting form for SAEs (SAE form) is not the same as the form in the AE section of the CRF. The two forms must be completed in a consistent manner, using the same medical terminology.

All AEs must be recorded on the e-CRF.

For the purposes of this study, the Coordinating Investigator will be in charge of reporting Suspected Unexpected Serious Adverse Reactions (SUSARs) considered to be related to the study treatment and SAEs to the Ethical Committees in the countries and other relevant ethical committees. DND*i* will be responsible for reporting SUSARs and SAEs to the regulatory authorities.

6.5.6. Grading of AE Severity

The severity of the AE must be graded according to NCI CTCAE, version 4.03 (38). For some biological parameters, the NCI CTCAE criteria have been adapted (i.e. hemoglobin, leucocytes, sodium, calcium, creatinine). If the AE is not described in the CTCAE, version 4.03, the Investigator will use the terms "mild", "moderate" or "severe" to describe the maximum severity, as defined below:

Mild	does not interfere with the patient's usual activities
Moderate	interferes to some extent with the patient's usual activities
Severe	significantly interferes with the patient's usual activities

The information concerning AE grading must be recorded in the AE section of the e-CRF.

It is important to distinguish between the severity and the seriousness of AEs: a severe AE is not necessarily an SAE.

6.5.7. Assessment of AE Causality

For all AEs, the Investigator is required to assess the possible causal relationship between the study treatment and the AE, with the help of the Coordinating Investigator as needed, in order to determine whether there is a reasonable possibility that the study treatment caused or contributed to the AE.

The causal relationship between the study treatment and the AE is assessed by the Investigator after a detailed analysis of the event in terms of the biological plausibility, taking into account possible unrelated causes, pre-existing medical conditions, concomitant treatments, the temporal relationship between intake of the study treatment and onset or worsening of the event, and known patterns of response to fexinidazole and NECT in general.

The two types of relationships are defined as follows:

- Unrelated: there is no temporal relationship between intake of the IP or reference treatment and the event, and/or there is a plausible alternative explanation;
- Possibly related: any AE that is not considered as unrelated to the study treatment and/or for which there is no plausible alternative explanation.

The decision to interrupt, resume or permanently discontinue study treatment due to an AE will be left to the discretion of the Investigator, except in situations described in Section 8 Withdrawal Criteria (57).

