1.2. Clinical Presentation of HAT

There are two successive stages in the clinical course of HAT. In the first stage, called the haemolymphatic stage or early stage, trypanosomes are present in the blood and lymphatic system. The clinical signs and symptoms are mild and non-specific, including intermittent fever, headache, pruritus and lymphadenopathy. The signs and symptoms are very similar to those of malaria, which explains why patients with early-stage HAT are often misdiagnosed with malaria. If it is not diagnosed and treated, HAT will progress to the next stage, called the meningoencephalitic stage or late stage, in which parasites invade the central nervous system. At this stage, patients display the classic neurological signs and, eventually, coma and death (3, 33, 49).

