1.7. Safety and Tolerability in Healthy Volunteers

Fexinidazole has been investigated in three phase-I studies in healthy volunteers of sub-Saharan African origin (15). In all studies, the subjects were closely monitored, with physical examinations, vital signs, electrocardiogram (ECG) and safety laboratory tests, as well as pharmacokinetic sampling performed before, during and after dosing. A total of 118 subjects were randomised in these studies. Single doses ranged from 100 mg to 3600 mg, and multiple doses from 1200 mg to 3600 mg for a maximum of 14 days.

Administration of fexinidazole in healthy volunteers was safe when given as a single dose or as repeated doses for 14 days. As with all nitroimidazole drugs, fexinidazole primarily affects the central nervous system (CNS) and gastrointestinal system, and can cause headache and/or vomiting or other mild to moderate gastrointestinal symptoms. At the highest dose, two subjects experienced prolonged anxiety with an episode of panic attack, associated with nausea and vomiting. No specific treatment was needed. Both subjects returned to normal within 2 to 3 days after stopping the investigational product (IP).

Fexinidazole is highly metabolized. As expected with this pharmacological class, a marked, transient, quickly reversible increase in liver enzymes was observed in one volunteer just after 14 days treatment at the highest dose. Data from these studies also suggest that there is a relationship between the dose used, as well as overall exposure (dose and duration), and the frequency and severity of abnormalities on liver function tests. These effects will be closely monitored during the study.

Another important laboratory finding was an increase, within the normal range, in plasma creatinine levels in subjects receiving the active treatment. This effect was not dose-dependent and is believed to be related to inhibition of renal tubular creatinine secretion, an effect that has previously been reported with nitroimidazole drugs (21). It is always reversible and is not accompanied by any other abnormalities on kidney function tests.

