Treatment-related serious adverse events			x	x	x	x	х	x	х	x	x	x	х	x	x	x (up to 24 months)
Recording of concomitant medication	x	х	х	х	х	х	х	х	х	х	х	х	х	х	х	
Dry blood spot sampling										x D8 H3.15	x D9H3	x D10H3 D10H7.15	x D10H24	x D10H48		
CSF sampling													x D10H24			

Table 5 – Overview of Protocol-planned Analyses

Analysis	Patients (n) (ITT)	Timepoint	Efficacy endpoints	Stopping Rules \blacklozenge π : actual responder rate p: observed responder rate	Power Chances of stopping the study due to actual responder rate (exact power)	Chances of stopping the study unduly (exact probabilities)
Futility analysis 1 Performed if the number of responders is ≤ 26/30 patients	20 (fexi) 10 (NECT)	End-of- Treatment Visit	Responder = no evidence of trypanosomes* at end of treatment	Unacceptable limit: π fexi < 95% = worse than melarsoprol (published results on responder rate at end of treatment p= 95.2% for melarsoprol; n= 6840) Stop if p fexi ≤ 80% Or if the number of responders is ≤16 out of 20 patients	58.9% if π fexi = 80% 77.5% if π fexi = 75% 89.3% if π fexi = 70%	1.59% if π fexi = 95% 0.0043% if π fexi = π NECT = 99%
Futility analysis 2 Performed if the number of responders is ≤ 97/105 patients	70 (fexi) 35(NECT)	End-of- Treatment Visit	Responder = no evidence of trypanosomes* at end of treatment	Unacceptable limit: π fexi < 95% (historical responder rate for melarsoprol) with π NECT \ge 99% (expectation for NECT and eflornithine) Or if the difference between the responder rates is > 4% in favour of NECT: $\pi_{NECT} - \pi_{Fexi} > 4\%$ Stop if Rule 1: p fexi $\le 88.57\%$ ($\le 62/70$) and p NECT $\ge 94.29\%$ ($\ge 33/35$) OR Rule 2: p NECT - p Fexi $\ge 15.7\%$ and p NECT $< 94.2\%$ ($< 33/35$) (Rule 2: modified Blackwelder test)	Rule 1 40.1% if π fexi = 90% 84.3% if π fexi = 85% 98.0% if π fexi = 80% Rule 2 29% if π fexi = 85% and π NECT = 98% 63.2% if π fexi = 80% and π NECT = 98%	Rule 1 2.33% if π fexi = 95% 0.0000% (if π fexi = 99%) Rule 2 0.08% (if π fexi = 95% and π NECT = 98%) 0.02% (if π fexi = 95% and π NECT = 97%) Note: the probability of applying Rule 2 is low (0.5%) if NECT \approx efformithine

Analysis	Patients (n) (ITT)	Timepoint	Efficacy endpoints	Stopping Rules \blacklozenge π : actual responder rate p: observed responder rate	Power Chances of stopping the study due to actual responder rate (exact power)	Chances of stopping the study unduly (exact probabilities)

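### Section 6.5.7 lets a plausible alternative explanation alone make an AE unrelated, against its own test of contribution; the two categories also overlap, and Table 4 labels its AE rows as treatment-related only

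*Protocol*

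**What the plan says.** Protocol section 6.5.7 gives the purpose of the causality assessment: to "determine whether there is a reasonable possibility that the study treatment caused or contributed to the AE". The investigator is to reach the answer by "taking into account possible unrelated causes, pre-existing medical conditions, concomitant treatments, the temporal relationship between intake of the study treatment and onset". Biological plausibility and what is known of how patients respond to either treatment are to be weighed as well.

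Only two answers are then allowed. The negative one reads "Unrelated: there is no temporal relationship between intake of the IP or reference treatment and the event, and/or there is a plausible alternative explanation", so either condition is enough to satisfy it. The positive one is partly defined by reference back to the negative one, and reads "Possibly related: any AE that is not considered as unrelated to the study treatment and/or for which there is no plausible alternative explanation".

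Relatedness feeds a stated safety endpoint. Sections 2.2.2 and 6.5 both list treatment-related AEs in the observation period, for all grades and for grade 3 or higher.

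On recording, section 6.5.4 requires every AE in the collection period to go into the e-CRF "whether or not they are considered to be treatment related", and section 6.5.5 repeats that all AEs are recorded. In Table 4 (Appendix 4), however, the two event rows are limited to treatment-related events; the second reads "Treatment-related serious adverse events" and runs to 24 months.

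**The concern.** A test that accepts contribution allows for more than one cause. A definition that a single plausible alternative can satisfy does not. The two stand in the same section, and the site has to enter one answer.

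The conflict matters in this population because the disease supplies a ready alternative for some of the drug's known effects. Section 1.7 says fexinidazole mainly affects the CNS and gastrointestinal system and "can cause headache and/or vomiting or other mild to moderate gastrointestinal symptoms". Section 1.2 lists "intermittent fever, headache, pruritus and lymphadenopathy" for the first stage of HAT and neurological signs for the late stage. Section 14.2.4 describes psychological and behavioural disturbances as frequent enough in HAT that excluding such patients could endanger completion of the study.

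Investigators know the treatment (section 5.7), so loose wording leaves room for different sites to class similar events differently. Section 1.10 says that this is a single pivotal study, randomised 2:1 to gather as much fexinidazole safety data as possible. A causality rule that conflicts with its own purpose weakens one of the safety outputs the design was chosen to provide.

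**Working it through.** The plan states no figure for this point, so the check is logical. Let T mean that a temporal relationship exists, and A that a plausible alternative explanation exists. Both definitions come from section 6.5.7:

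- Unrelated = (not T) or A
- Possibly related = (not Unrelated) or (not A)

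| T | A | Unrelated? | Possibly related? | Result |
|---|---|---|---|---|
| yes | yes | yes | no | Unrelated only |
| yes | no | no | yes | Possibly related only |
| no | yes | yes | no | Unrelated only |
| no | no | yes | yes | Both |

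Two separate faults follow.

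1. **T yes, A yes.** The event follows dosing and another cause is also plausible. The contribution test leaves relatedness open; the definition closes it as unrelated. A headache after a dose in a patient with HAT falls here. The fault comes from the and/or in the definition of *Unrelated*.
2. **T no, A no.** The event meets both definitions, so the categories are not mutually exclusive in 1 of the 4 cells. HAT-like events are not in this cell, because for them A is yes.

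The consequences can be traced through the sections that use, or do not use, the answer:

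| Item | Protocol section | Depends on relatedness? |
|---|---|---|
| Treatment-related AE endpoint | 2.2.2, 6.5 | Yes |
| SUSAR classification | 6.5.5 | Yes |
| Reporting of non-serious AEs after discharge | 6.5.4; 5.8.4 leaves other follow-up events in the medical file only | Yes |
| Follow-up of non-serious AEs beyond study participation | 6.5.9 | Yes |
| SAE report to the monitor within 24 hours | 6.5.5 | No |
| SAE reports to ethics committees and authorities | 6.5.5 | No |
| SAE collection from consent to 24 months | 6.5.4 | No |
| Endpoints for all AEs, AEs of grade 3 or higher, and SAEs | 2.2.2, 6.5 | No |

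Table 4 is a further, independent mismatch. Its two row labels restrict events to those judged treatment-related, while sections 6.5.4 and 6.5.5 require all of them.

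**The case against.** The strongest reply is that the definitions should not be read alone. The paragraph above them asks for a detailed analysis of several factors, with the Coordinating Investigator's help where needed, so a careful investigator would not call every post-dose headache unrelated. This stands as far as it goes: misclassification is a risk of the literal wording, not a certainty. It does not remove the conflict, because the two definitions are the only answers available and one of them contradicts the purpose just stated.

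Several limits on the consequences also stand.

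- In-hospital events stay in the all-cause endpoints whatever their causality, and worsening of listed baseline signs and symptoms counts as an AE. Section 9.9 describes analyses of SAEs, AEs leading to discontinuation and all AEs; causality appears there only in the SAE narratives.
- The rule applies equally to both arms, and nothing in the protocol shows a bias between them.
- The overlap with HAT is partial. The headache quoted from section 1.2 belongs to the early stage. The prolonged anxiety in sections 1.7 and 1.9 arose at the highest dose and in the stopped 2400 mg cohort, not with the regimen chosen here. Liver-enzyme, creatinine and QTcF findings do not resemble the HAT symptoms described.
- The overlap cell should seldom matter for the treatment-related endpoint, since the observation period ends at most 8 days after treatment.

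A reader might infer that HAT-like events escape expedited reporting. Section 6.5.5 does not support that: every SAE goes to the monitor within 24 hours, and SAEs as well as SUSARs go to ethics committees and authorities. Only the SUSAR label can change. A reader might also blame the overlap for the loss of HAT-like events, but the truth table places them in a different cell.

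**Conclusion.** Wrong as written. The definition of *Unrelated* contradicts the section's own test in one of the four combinations, and the two categories overlap in another. Read literally, AEs that HAT could also explain may be under-counted in the treatment-related AE endpoint and may not be classed as SUSARs. If they are non-serious and occur after discharge, they may go unreported or not be followed beyond study participation. Table 4 separately contradicts the rule that all AEs and SAEs are recorded.

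The size of any under-count cannot be computed, because the protocol gives neither AE rates in patients nor the share of events for which HAT would be judged a plausible alternative. Any assumed share would simply reappear as the share lost. It would also be too strong to conclude that sites will filter events by the Table 4 labels, since the body text tells them otherwise; the labels only make that error possible.

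The conclusion rests on a literal reading of and/or, under which either condition is enough.

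**What to change.** In section 6.5.7, replace the two definitions with exclusive ones that follow from the stated test, for example:

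- *Possibly related*: a causal or contributory role of the study treatment is reasonably possible, including when another cause is also plausible.
- *Unrelated*: no such role is reasonably possible.

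Timing and alternative causes then remain factors to weigh, and neither decides the answer by itself.

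In Table 4, rename the two rows *Adverse events (all)* and *Serious adverse events (all)*, to agree with sections 6.5.4 and 6.5.5.

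The cost is a few lines of protocol wording and a site training note. The reported treatment-related AE rate will be somewhat higher, because events with two plausible causes will now count as possibly related. Visits, treatment and sample size do not change.

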6.5.8. Exposure *in utero*

Three pregnancy tests are planned during the study: prior to randomisation, at discharge and at the 3-month visit. Among women of child-bearing potential, only those who have a negative result on the pregnancy test prior to randomisation will be eligible to participate in the study.

The Investigator must report any pregnancy that occurs during the observation period of the study, or that is diagnosed at the 3-month follow-up visit, using the appropriate pregnancy reporting form. This must be done irrespective of whether an AE occurred or not. If known, the due date must be specified.

The Investigator will monitor the patient until the term of the pregnancy, i.e. full term or preterm, in the event of a miscarriage. The Investigator will provide information on the outcome of the pregnancy using the pregnancy follow-up reporting form.

A physician, preferably a paediatrician, should examine the infant at birth and submit a report using a pregnancy follow-up reporting form. The Investigator will offer the parents follow-up on infants exposed to the study treatment *in utero* until they reach 24 months of age. As far as possible, stillborn infants should be examined by a physician to assess the cause of death.

6.5.9. Follow-up on AEs

All AEs must be followed until resolution, or until the Investigator considers them to be "chronic" or "stable", or until the patient's participation in the study ends, i.e. until the final report is completed for the study in which the patient was participating.

If the AE is a laboratory abnormality with a toxicity grade \geq 3, the test must be repeated 2 to 4 days later, and then at regular intervals until the parameter reaches toxicity grade \leq 1, or until it returns to the baseline level (see Baseline Assessment).

In addition, all SAEs and all events that the Investigator (and the Coordinating Investigator or the monitor, as needed) considers as possibly related to the study treatment must continue to be followed even after the end of the patient's participation in the study. Such events should be followed until their resolution, or until the Investigator considers them as "chronic" or "stable." The resolution of such events must be documented in the e-CRF, and if they are SAEs, on an SAE follow-up form.

7. Study Duration

The enrolment period is expected to last 18-20 months (see Table 7 – Expected Enrolment Rate; p 104). The duration of treatment will be 10 days in both treatment groups.

Each patient's participation will last approximately 25 months and will include:

- pre-treatment period (pre-screening and screening, treatment of concurrent disease)
- treatment period of 10 days
- hospitalisation for 3 to 8 days after treatment
- out-patient follow-up for 18 months, until the TOC visit

• additional follow-up for 6 months, until M24

The total duration of the study, including the preparative phase, is expected to be 48 months.

8. Withdrawal Criteria

8.1. Rules for Temporary Interruption of Treatment

Temporary interruption of treatment will not necessarily lead to withdrawal of the patient from the study. In some cases, treatment may be interrupted for a maximum of one day, i.e. one missed dose of fexinidazole or 3 missed doses of NECT, and treatment will therefore be delayed. Treatment may be reintroduced at the discretion of the Investigator responsible for the patient. One additional day of treatment will be added to make up for the missed dose (or doses as concerns NECT). The patient should continue the visits and study procedures as planned, taking into account the delay. The reasons for interrupting treatment must be recorded in the appropriate source documents and e-CRF.

8.2. Rules for Definitive Discontinuation of Treatment

The Investigator will discontinue the study treatment in the following cases:

- Severe skin reaction
- ALAT or ASAT exceeding 8 x ULN
- ALAT or ASAT exceeding 3 x ULN associated with total bilirubin > 2 x ULN
- ALAT or ASAT exceeding 3 x ULN accompanied by fatigue, nausea, vomiting, right upper quadrant pain or tenderness, fever, rash, and/or eosinophilia (>5%)
- pre-dose QTcF measurement ≥ 500 ms on D2, D3, D4 or D4H23, confirmed by a second ECG recorded after at least a 10-20 minute rest
- Any condition that, in the opinion of the Investigator, requires treatment discontinuation for medical reasons.

If a patient is withdrawn from the study before the end of treatment, the physician will make all necessary arrangements to ensure that s/he receives the appropriate treatment for the condition in question.

